10.2 Secondary study parameter(s)

To analyse the association between the vaginal microbiome and PCOS compared to controls, the bacterial taxa will be first classified to the genus level. The relative abundance will be quantified based on each taxa contribution to an individual sample. Operational taxonomic unit (OTU) abundance will be noted for all samples. Alpha and Beta diversity will be calculated. Associations between the vaginal microbiome (Alpha and Beta diversity) and PCOS-associated variables as BMI, hirsutism, acne, testosterone, androstenedione, LH/FSH, insulin, will be tested in a linear regression model.

To investigate the association between the bacterial diversity and markers for gut permeability and inflammation in PCOS patients, a logistic regression model will be used. Leaky gut markers as calprotectin, zonulin, lipopolysaccharide and soluble CD15 and inflammation markers as CRP, IL-22, IL6 and TNF-a will be tested in the logistic regression model. Also the results of the Food Frequency Questionnaire (FFQ) will be analysed in the logistic regression model.

Differences on clinical characteristics and metabolic biomarkers will be evaluated using t-test or a one-way analysis of variance (ANOVA) for normally distributed variables or non-parameter Wilcoxon test for non-normally distributed variables. Two-sided tests will be used, and p-values less than 0.05 will be considered statistically significant.

As for the metabolomic analysis, the raw data will be pre-processed first. Log-transformation and centering are techniques used to make the data normal distributed. To investigate differences between the PCOS and controls, univariate analysis will be performed to examine each metabolite feature separately.

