10 STATISTICAL ANALYSIS

10.1 Primary study parameter(s)

Statistical analyses

The statistical analyses will be conducted using the statistical software R.

Continuous variables will be expressed as mean and standard deviation for normally distributed variables, median and interquartile range for not normally distributed variables.

To analyse the association between the gut microbiome and PCOS compared to controls, reads with some level of similarity will be grouped into operational taxonomic units (OTUs). Alpha and beta diversity analyses will be calculated to estimate the abundance and diversity of species within samples.

Alpha diversity comparisons will be analysed with Shannon diversity index and richness as continuous variables. Higher Shannon diversity index is associated with a more diverse and rich vaginal microbiome. It measures the number of species and the differences between species abundances. A logistic regression model will be used to test the changes of alpha diversity in PCOS and non-PCOS women. Same analyses will be conducted for changes of alpha diversity in overweight/obese and lean women with or without PCOS. Linear regression analyses will be conducted to study the correlation between the diversity of the microbiome (Alpha and Beta diversity) and parameters such as hyperandrogenism, rated as serum total testosterone level or Free Androgen Index (FAI). Other PCOS-associated variables included in the univariable linear regression analyses are: hirsutism, acne, BMI, LH/FSH, testosterone, androstenedione. Significant variables from the univariable regression analyses will be tested in a multivariable linear regression model. To correct for multiple testing, Bonferroni's correction will be conducted.

UniFrac will be used to compare the (dis-)similarities among the microbial communities samples (beta-diversity). Unweighted UniFrac analyses is based on presence/absence of difference taxa and abundances and weighted UniFrac will take the abundances of different taxa into consideration. The results from Unifrac analyses will be represented using Principal Coordinate Analysis (PCoA) plots. PCoA plots will represent the dissimilarity of microbiome samples. The PCoA will be based on the overall structure of the gut microbiome in all samples for PCOS and controls.

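### Section 10.2 assigns logistic regression to diversity versus gut-permeability and inflammation markers within PCOS patients, where model, question and population do not fit together

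*Protocol*

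**What the plan says.** All references are to the protocol.

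- Section 10.2, question, population and model: for bacterial diversity and "markers for gut permeability and inflammation in PCOS patients, a logistic regression model will be used".
- Section 10.2, variables: calprotectin, zonulin, lipopolysaccharide and soluble CD15 are listed as leaky-gut markers, and "inflammation markers as CRP, IL-22, IL6 and TNF-a will be tested in the logistic regression model". The next sentence adds: "Also the results of the Food Frequency Questionnaire (FFQ) will be analysed in the logistic regression model".
- Section 10.2, sentence immediately before, for the vaginal microbiome: "PCOS-associated variables as BMI, hirsutism, acne, testosterone, androstenedione, LH/FSH, insulin, will be tested in a linear regression model".
- Section 10.1, scale of diversity: "Alpha diversity comparisons will be analysed with Shannon diversity index and richness as continuous variables".
- Section 10.1, logistic models: "A logistic regression model will be used to test the changes of alpha diversity in PCOS and non-PCOS women", and "Same analyses will be conducted for changes of alpha diversity in overweight/obese and lean women with or without PCOS".
- Section 10.1, gut diversity against clinical variables: "Other PCOS-associated variables included in the univariable linear regression analyses are: hirsutism, acne, BMI, LH/FSH, testosterone, androstenedione".

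Section 3 plans 50 overweight/obese and 50 lean women with PCOS, and the same numbers of controls. Section 8.3 lists the permeability and inflammation markers as laboratory measurements, without thresholds.

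**The concern.** Logistic regression needs a binary outcome. The question in 10.2 is whether two measured quantities, diversity and a marker, go together among women who all have PCOS. The text fixes the model and the population, but neither the variables in the question nor the case status behind the 10.1 logistic model gives a binary outcome that varies in that population.

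The analyst would have to settle this after the data are in: change the model, add the controls, or cut a continuous variable at a point the protocol does not give. These choices answer different questions or differ in power. A later analysis plan that follows 10.2 literally inherits the conflict; one that departs from it contradicts the protocol.

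**Working it through.** The protocol gives no effect size, power or event count for this analysis, so there is no figure to reproduce. The check is mainly one of logic.

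**Step 1. Try each possible outcome against the text of 10.2.**

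| Possible outcome | Binary? | Varies among PCOS patients? | Estimates diversity versus marker? |
|---|---|---|---|
| Alpha diversity (Shannon, richness) | No, continuous by 10.1 | Yes | Yes, but not by logistic regression |
| A permeability or inflammation marker | No, assay value without cut-off (8.3, 10.2) | Yes | Yes, but not by logistic regression |
| PCOS status (10.1 logistic model) | Yes | No, constant | No |
| BMI group (50 v 50, section 3) | Yes | Yes | No; models BMI group, and 10.2 does not name it |
| Hirsutism or PCOM, yes/no (section 12.1) | Yes | Yes | No; models a clinical feature, and 10.2 does not name it |
| PCOS versus control | Yes | Needs the controls | No; relates diversity and markers to PCOS status |

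No row meets all the requirements of the sentence. As a check on the third row, a logistic model was fitted to 100 simulated women all coded as cases. It gave standard errors of about 63,000 to 74,000, so nothing is estimable.

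**Step 2. Compare with the protocol's own choice for the parallel question.** For diversity against testosterone, androstenedione, BMI and LH/FSH, linear regression is named in both 10.1 and 10.2. Insulin is added in 10.2 only. No reason is given for a different model for the markers.

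**Step 3. Illustrate the cost of forcing the logistic model by a median split.**

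Inputs: n = 50 + 50 = 100 women with PCOS (section 3); two-sided 0.05 (10.2), without Bonferroni adjustment. The correlation r is assumed, because the protocol gives none. The median split is also an assumption; the protocol does not mention one.

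Approximation: power ≈ Φ(atanh(r) × √(n − 3) − 1.96). For a median split, n is replaced by n × 2/π = 100 × 0.6366 = 63.7.

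For r = 0.28, atanh(r) = 0.2877:
- Linear: 0.2877 × √97 − 1.96 = 2.833 − 1.96 = 0.873, so power ≈ 81%.
- Median split: 0.2877 × √60.7 − 1.96 = 2.241 − 1.96 = 0.281, so power ≈ 61%.

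Simulation (bivariate normal, 10,000 replicates) beside the approximation:

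| Assumed r | Linear, simulated | Split logistic, simulated (Wald to likelihood ratio) | Approximation, linear / split |
|---|---|---|---|
| 0.20 | 52% | 34-37% | 52% / 35% |
| 0.28 | 81% | 60-63% | 81% / 61% |
| 0.35 | 95% | 80-82% | 95% / 81% |

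The two methods agree. The loss is between about 13 and 21 percentage points over this range, and it arises only if a continuous variable is dichotomised.

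**The case against.** The best defence is that 10.2 extends the logistic model of 10.1. The outcome is then PCOS status, the controls are available, and the model runs. The protocol is also loose about the population elsewhere. The objective on gut-vaginal correlation concerns PCOS patients alone in the Summary, but PCOS patients and controls in section 2. This reading is plausible, and the documents do not exclude it. It does not remove the point: the restriction to PCOS patients would then be wrong, and the question would become diversity and markers versus PCOS status. The text needs changing on either reading.

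A second objection is that the dependent variable, cut-offs and the role of the FFQ are details for a statistical analysis plan, which is not at hand. That stands as far as it goes, and their absence alone would be no finding. What remains is a model that the protocol does state and that conflicts with the population and question it states beside it.

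A third is that the consequence is small. That also stands. The markers are not among the main or secondary parameters in 8.1.1 and 8.1.2.

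A reader might infer three stronger things, none of which the documents support:
- That the logistic model in 10.1 is invalid too. It is not on this ground: PCOS versus non-PCOS is binary and both groups are recruited.
- That the trial will lose about 20 points of power here. The protocol plans no median split and gives no correlation, and the loss does not arise in a comparison with controls.
- That 10.2 certainly intended a within-PCOS analysis and chose the wrong model. The error may equally lie in the wording of population and question.

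**Conclusion.** The point holds as a conflict within section 10.2: logistic regression, a diversity-marker question and a PCOS-only population cannot all stand. Which of the three is the slip cannot be decided from the document.

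The analysis affected is supportive. The primary endpoint, the listed secondary endpoints, the sample size and every stated figure are unaffected. The conflict itself rests on no numerical assumption. The power illustration rests on an assumed correlation, bivariate normality, 100 complete PCOS patients, an unadjusted 0.05 level and a median split. It shows what one workaround would cost, not what the plan will lose. The correction should be made, but it is not critical to the trial's main conclusions.

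**What to change.** In 10.2, state the outcome and the population, and match the model to them.

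- **If the association within PCOS patients is meant:** replace logistic with linear regression. Take the diversity index (Shannon, richness) as continuous outcome and each permeability or inflammation marker as continuous predictor, log-transformed or rank-based if skewed. Enter the FFQ results as covariates in that model. This agrees with the linear models already named for the clinical variables.
- **If PCOS versus control is meant:** keep logistic regression, name PCOS status as the outcome and say that the controls are included. Delete the restriction to PCOS patients, and word the question as diversity and markers versus PCOS status.

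The cost is the rewording of the three sentences in 10.2 that name logistic regression. No new data, samples or participants are needed; section 8.3 already takes controls through the same screening and the study procedures.

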After collection the vaginal swab and stool sample will be split in different portions to be analysed using the 16S rRNA gene sequencing. In both the stool and vaginal swab samples the following parameters will be measured: both the microbiome profile patterns (three different groups of microorganisms: (1) Firmicutes/ Actinobacteria/ Verrucomicrobia (2) Bacteroidetes and (3) Proteobacteria) by the NGS and another high throughput technique for the Lactobacillus, Staphylococcus, E coli and Bacillus RG4 composition as percentage of the total microbiome content.

16S ribosomal RNA amplicon sequencing

Both gut and vaginal microbiome will be analysed by using 16S ribosomal RNA sequencing (rRNA). For each sample the V4 hypervariable region of the 16S rRNA gene will be amplified by polymerase chain reaction (PCR) with primers. The steps in the PCR process are as follow and each step occurs at a different temperature. First denaturation at 94°C occurs and the two DNA strands get separated out. Then amplification at different temperatures occurs. Finally, the enzyme Polymerase is added which make the primers extend along the length of the DNA strand.

Laboratory measurements includes: estradiol, total testosterone, androstenedione, dyhydroepiandrosterone (DHEA), dehydroepiandrosterone sulfate (DHEAS), dehydrotestosterone (DHT), serum cortisol, thyroid-stimulating hormone (TSH), prolactin, insulin, anti-Muellerian hormone (AMH), sex hormone-binding globulin (SHBG), serum luteinizing hormone (LH), follicle-stimulating hormone (FSH), 17-hydroxyprogesterone (17OH-P), plasma total cholesterol, high-density lipoprotein (HDL)- cholesterol, triglycerides and glucose. These laboratory measurements are already included in the COLA screening. Addition measurements that will be obtained include but will not limited to: LH, FSH, estradiol, progesteron, hsC-reactive protein (CRP), interleukin-22 (IL-22), IL6, tumor necrosis factor-a (TNF-a), serum endotoxin (=lipopolysacharide, LPS), adiponectin, serum zonulin, sCD14: soluble CD14 (endotoxin co-receptor), bile acids in serum and in stool, stool calprotectin and stool zonulin.

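### Section 10.2 sets a flat p<0.05 rule and tests metabolite features one at a time, while the only multiplicity correction, in section 10.1, has no stated scope and is not carried over.

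*Protocol*

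**What the plan says.** Three statements in the protocol bear on this point.

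- **Section 10.2, marker paragraph.** Group differences in clinical features and metabolic markers are assessed by t-test or one-way ANOVA when normally distributed, "or non-parameter Wilcoxon test for non-normally distributed variables". The decision rule follows: "Two-sided tests will be used, and p-values less than 0.05 will be considered statistically significant". No other significance threshold appears in the protocol.
- **Section 10.2, metabolomics paragraph.** After pre-processing, PCOS patients and controls are compared feature by feature: "univariate analysis will be performed to examine each metabolite feature separately". The paragraph gives no threshold, no number of features and no error-rate method.
- **Section 10.1.** The paragraph on alpha diversity and on the univariable and multivariable regressions ends with "To correct for multiple testing, Bonferroni's correction will be conducted". It defines no family of tests and states no overall alpha. Section 10.2 does not refer to it.

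The laboratory measurements are listed in section 8.3, in two panels. Of the first it says "These laboratory measurements are already included in the COLA screening". The second is open-ended: "Addition measurements that will be obtained include but will not limited to".

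**The concern.** The metabolic profile of PCOS is a named secondary objective and endpoint (sections 2 and 8.1.2). Section 1 gives its purpose as finding candidate biomarkers and targets for later research. The natural output is therefore a list of features that pass a threshold, and what that list is worth depends on the threshold.

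The protocol allows two readings. If Bonferroni belongs to 10.1 alone, the marker and metabolite tests run at 0.05 each with nothing to limit false positives. If Bonferroni is meant to cover the whole study, the unqualified 0.05 rule in 10.2 conflicts with it. The two readings would give very different lists from the same data, and the text leaves room to choose between them after the results are seen.

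There is also a smaller gap in the same paragraph. ANOVA is provided for more than two groups, but the only rank test named is Wilcoxon, which compares two. The design has four PCOS-by-BMI groups (section 3), and Supplementary I lists four phenotypes. A skewed variable compared across such groups has no named test.

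**Working it through.** The plan has no derived figure to reproduce: 0.05 is an input, and section 4.4 bases the sample size on sample availability and literature, without an effect size, standard deviation, alpha or power.

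**Inputs from the protocol.** Two-sided 0.05 per test (10.2); 100 PCOS patients and 100 controls (section 3).

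**Inputs assumed.** Number of features; share of features that truly differ (π); power per test. For scale, 100 v 100 at two-sided 0.05 gives power of about 0.29, 0.81 and 0.94 for standardised differences of 0.2, 0.4 and 0.5 (normal approximation).

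**Expected false hits.** 0.05 × number of null features:

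- 100 null features: 0.05 × 100 = 5
- 200: 10
- 500: 25
- 1000: 50

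**False share of the significant list.** (1 − π) × 0.05 / [(1 − π) × 0.05 + π × power]. At 80% power:

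- π = 5%: 0.0475 / (0.0475 + 0.04) = 54%
- π = 10%: 0.045 / (0.045 + 0.08) = 36%
- π = 20%: 0.04 / (0.04 + 0.16) = 20%
- π = 50%: 0.025 / (0.025 + 0.40) = 6%

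Over a wider range of assumptions:

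| Truly different | Power 0.3 | Power 0.5 | Power 0.8 | Power 0.94 |
|---|---|---|---|---|
| 1% | 94% | 91% | 86% | 84% |
| 5% | 76% | 66% | 54% | 50% |
| 10% | 60% | 47% | 36% | 32% |
| 20% | 40% | 29% | 20% | 18% |
| 50% | 14% | 9% | 6% | 5% |

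The share does not depend on the number of features, only on π and power.

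**How far the two readings differ.** For a standardised difference of 0.5 at 100 v 100, power is 0.94 at 0.05. Under Bonferroni over an assumed 500 features (0.05/500 = 0.0001) it is 0.36. The scope of one sentence therefore decides whether most such features are found or most are missed.

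**Laboratory markers.** Section 8.3 lists 19 in the screening panel and 16 additional ones, of which LH, FSH and estradiol repeat: 19 + 16 − 3 = 32 distinct names. If all 32 were tested at 0.05, all were null and all were independent, 32 × 0.05 = 1.6 false hits would be expected, and the chance of at least one would be 1 − 0.95^32 = 0.81. For the 19 screening markers alone it would be 1 − 0.95^19 = 0.62. These figures are illustrative only, because none of the three conditions is met for certain.

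**The case against.** The strongest reply is that this is silence and not error. The 0.05 rule closes the marker paragraph, the metabolomics paragraph states no threshold, and a statistical analysis plan that is not at hand may well set the error-rate method for metabolites. Section 10.1 also opens with study-wide statements on software and data summaries, and it names Bonferroni without an alpha. The only alpha is in 10.2, so the two sections could be read together.

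Part of this stands. Applying 0.05 to metabolite features is an inference, and the missing metabolomics method would be no finding by itself. What remains is what the protocol does state: an unqualified per-test rule in one section, an unscoped correction in another, and nothing to connect them.

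A reader might infer more than the text supports:

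- **That about half of the reported metabolites would be false.** This is one point in a range of about 5% to 94%. It needs, for example, about 6% of features truly different at 80% power. The protocol supplies neither input, and its own background cites a study in which every measured fatty acid was raised, which does not suggest sparse signal.
- **That section 10.2 tests 32 markers with an 81% chance of a false hit.** The list is in 8.3. Section 10.2 never says that all are compared singly, and it places eight leaky-gut and inflammation markers in a logistic model. Testosterone and the Free Androgen Index help to define PCOS in Supplementary I, and controls must meet no Rotterdam criterion, so those differences are built in. Other markers are likely to be correlated.
- **That skewed markers would go through six pairwise Wilcoxon tests.** Simulated for four groups of 50, that procedure gives roughly 19% false positives per marker, but no section prescribes it. The supported point is only that no rank test for more than two groups is named.

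**Conclusion.** The point holds at moderate severity. Taken as written, the marker comparisons and the feature-by-feature metabolite tests have no control of false positives, and the relation between the 0.05 rule in 10.2 and the Bonferroni sentence in 10.1 is undefined. The firm figure is about 5 expected false hits per 100 truly null features, if 0.05 is applied to each. The false share of the resulting list rests on assumptions about signal density and power, and should be quoted only as a range.

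It would go too far to say that the metabolic conclusion will be wrong or dominated by chance. That is so if few features differ, and not so if many do. The primary comparison of the gut microbiome between patients and controls does not depend on these tests, so the study's main conclusion is not at risk.

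**What to change.** Amend the wording of the statistical section before the data are analysed:

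1. In 10.2, call metabolite features significant at a Benjamini-Hochberg false discovery rate of 5%, and report q-values. This limits the expected false share of the list to about 5%, and costs less power than Bonferroni over hundreds of features.
2. Apply the same rule, as a separate family, to the laboratory markers compared between groups. List those markers, and leave out the androgen measures that define PCOS: their near-certain rejection would loosen the threshold for the rest.
3. Restrict the flat 0.05 rule to single tests named in advance.
4. State in 10.1 that Bonferroni covers the regression tests of that section.
5. Name Kruskal-Wallis for skewed variables when more than two groups are compared.

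Adjusting each metabolite model for BMI group or age is a separate modelling decision and is not needed to settle this point.

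The change needs no new data, only revised text and a few lines of R. The downside is a shorter list of significant markers and metabolites.

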10.3 Other study parameters

Not applicable

10.4 Interim analysis (if applicable)

Not applicable

11. ETHICAL CONSIDERATIONS

11.1 Regulation statement

The investigators will ensure that this study is conducted in agreement with the Declaration of Helsinki (version of October 2013, www.wma.net) and all relevant national guidelines and regulations, whichever provides the greatest protection for the patient. The study protocol will be submitted to the ethics committee.

11.2 Recruitment and consent

Women who are eligible for the study will be informed by the clinician about the the GuVa PCOS study and when the patient is interested in participation, the main investigator will contact the patient. The main investigator will inform the patient. about the voluntary nature of their participation as well as by means of the information leaflet and informed consent form. Full comprehensive information will be given to all patients according to the regulations of the competent authorities that need to approve the clinical study. Participants in the control group will be recruited via online advertisement and via the outpatient clinic of Reproductive medicine.

Informed consent:

The study will be performed according to written informed consent procedures and this study protocol that are approved by local and/or national ethics committees. The informed consent procedures ensure personal data protection and confidentiality. Data will be coded, i.e. information will not be directly traceable to an individual person.

Patients who signed the informed consent, agree on sharing unexpected findings with the specialist or general practitioner. Patients who do not want their physician and or general practitioner to be informed about the following, cannot participate in the study.

